3.1.1 Adult Population

3.1.1.1 Adult Stage 1

Stage 1 of this trial will enroll up to a maximum of 900 adult study participants (up to 60 participants per arm). The trial initially focused on adults with at least 1 of 5 autoimmune diseases: SLE, RA, MS, SSc, and pemphigus.

Participants will be assigned to 1 of 3 cohorts based on their IS regimens:

- Cohort A: Receipt of MMF or MPA (\pm other rheumatic disease medications, including biologics)
 - Participants who are taking MMF or MPA (without additional B cell depleting medications or MTX) will be placed in this cohort.
- Cohort B: Receipt of MTX (\pm other rheumatic disease medications, including biologics)
 - Participants who are taking MTX (without additional B cell depleting medications or MMF/ MPA) will be placed in this cohort.
- Cohort C: Receipt of BCDT within the past 18 months (\pm other rheumatic disease medications)
 - Participants taking B cell depletion medications, regardless of whether they are also taking MMF or MTX, will be placed in this cohort.

Treatment Arms: Participants in Cohorts A, B, and C will be assigned to receive an additional dose of the same COVID-19 vaccine as their original vaccine series.

Participants in Cohorts A and B will be randomized into 2 IS medication treatment plans as follows:

- Participants continue to take their IS medications without alterations in schedule and dosing.
- Participants withhold their cohort-defining IS medications before and after the additional homologous vaccine dose per protocol instructions (see Section 7.1.1 Protocol-mandated Medications).

All potential treatment arms for Adult Stage 1 are detailed in [Table 2](#).

Update: Arms to receive an additional homologous vaccine dose after an initial Janssen COVID 19 Vaccine were closed to enrollment after the CDC updated its recommendations to express a clinical preference for individuals to receive an mRNA COVID-19 vaccine over the Janssen COVID-19 vaccine. All Adult Stage 1 treatment arms were closed to enrollment on 15 August 2022.

Schedule of Events: Visits to assess endpoints will occur at Baseline (Week 0), Week 4 \pm 1 week, Week 12 \pm 2 weeks, Week 24 \pm 2 weeks, Week 36 \pm 2 weeks, and Week 48 \pm 2 weeks. Participant and study flow diagrams are provided in Figure 1 and Figure 2, respectively.

An Adult Stage 1 participant will be enrolled in the study for a maximum of approximately 13 months.

[figure not shown]
Table 2. Treatment Arm Assignments in Adult Stage 1

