13.4.4 Analyses of Secondary and Other Endpoint(s)

For Stage 1, the multivariable logistic and linear regression models defined in Section 13.4.3 Supportive Analyses of the Primary Endpoint above will be used to compare response to additional homologous doses of COVID-19 vaccine for a variety of subgroups. Appropriate contrasts will be defined to compare vaccine response for the following:

- Continuing versus withholding IS medications will be compared within cohort (cohorts A and B only) and within and across type of vaccine.
- The types of additional vaccine dose administered will be compared within cohorts and across cohorts, and within and across IS treatment plan groups.
- Type of IS medications will be compared within and across each type of vaccine.
- Age groups and type of disease will be compared within and across each type of vaccine.
- Corticosteroid dose at baseline will be added as a covariate to the model to assess impact on vaccine response.
- Immune response to the initial COVID-19 vaccine regimen will be assessed within and across each type of vaccine.
- Additional covariates for disease activity, co-morbid illness, age, and sex may be added to assess whether the clinical parameters are associated with response to additional vaccine dose.

Data for the Moderna COVID-19 Vaccine and Pfizer-BioNTech COVID-19 Vaccine may be combined in the comparisons above to assess the effect of mRNA vaccines together.

The incidence of seroconversion following additional vaccine doses of COVID-19 vaccine will be evaluated in the subgroups of participants that are anti-COVID-19 antibody negative at baseline using separately, (a) NIAID-VRC MSD 3 plex (Wu-1 full-length spike, RBD, and N proteins) assay with thresholds <1204.7 , 517.9 , and 9779.6 AU/mL, respectively, and (b) the Roche Elecsys® Anti-SARS-CoV-2 S electrochemiluminescence immunoassay with a threshold <0.80 U/mL. The proportions who seroconvert within and across arms will be summarized using 95% Clopper-Pearson confidence intervals, and comparisons will use a two-sample Binomial exact test with nominal two-sided alpha = 0.05.

For the subgroups of participants that are anti-COVID-19 antibody positive at baseline using separately, (a) the NIAID-VRC MSD 3 plex (Wu-1 full-length spike, RBD, and N proteins) assay, and (b) the Roche Elecsys® Anti-SARS-CoV-2 S electrochemiluminescence immunoassay with a threshold ≥ 0.80 U/mL. Fold improvement for each assay will be defined as:

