13.4.5 Descriptive Analyses

Summary descriptive statistics for baseline and demographic characteristics, disposition, and medication use will be provided for the safety and vaccinated populations. These data will be presented in the following manner:

- Continuous data (e.g., age, weight, and height) will be summarized by mean, standard deviation, median, and range.
- Categorical data (e.g., sex and race) will be presented as counts and percentages.

All medications taken by or administered to study participants beginning 30 days before the Screening Visit and continuing throughout the study will be collected. All medications used will be coded according to the World Health Organization (WHO) drug dictionary. The number and percentage of participants receiving prior and concomitant medications/therapies will be presented overall and by medication class.

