13.7 Sample Size Considerations

Early reports show that a significant number of individuals taking IS medications respond poorly or not at all to COVID-19 vaccination. Ruddy et al. reported 26% of chronic inflammatory rheumatic disease patients had undetectable SARS-CoV-2 antibody response after their first mRNA vaccine dose, but many seroconverted with the second dose such that only 6% had persistent undetectable SARS-CoV-2 RBD antibodies [16]. However, those taking MMF or rituximab were at much higher risk of not mounting a detectable antibody response (89% and 67%, respectively)[17]. Another report has demonstrated diminished overall serologic response in adults with chronic inflammatory diseases, particularly in those treated with B-cell depletion or antimetabolites including MTX, with a 50-fold and 3-fold reduction in post-vaccine antibody titers relative to immunocompetent controls[80].

Based on the emerging evidence in individuals taking IS medications, an ineffective rate of achieving a protective immune response after the additional vaccine dose was defined to be less than or equal to 0.25 (null hypothesis). The study is powered to reject the null hypothesis in each arm when the true response rate is 0.5 or greater as preliminary evidence the additional vaccine dose is effective in specific study population.

The proportion of participants in each arm (cohort, additional vaccine dose, and IS treatment plan group) to receive an additional vaccine dose and achieve a protective antibody response at Week 4 will be evaluated using a one-sided exact test with alpha = 0.05 to test against a null hypothesis that the true response rate is ≤ 0.25 . A sample size of 33 evaluable participants achieves at least 90% power to reject null hypothesis when the true response rate is 0.5 or greater.

Secondary analyses will compare the rate of achieving a protective immune response across arms using the multivariable logistic regression model. For comparisons of single arms, 33 evaluable participants per arm will provide 80% power to detect an odds ratio of 4.2 when the null hypothesis is true in one arm (improvement from 0.25 to 0.584). For comparisons that combine arms, pooling 3 arms (e.g., type of additional vaccine dose) will provide 80% power to detect an odds ratio of 2.3 (improvement to 0.394).

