6.2. Demographic and Other Baseline Characteristics

Summary descriptive statistics for baseline and demographic characteristics will be reported for all analysis samples by study arm. Characteristics to be summarized include:

- Age, race, ethnicity, sex, body weight at screening, height
- Disease type and duration
- Roche Elecsys® Anti-SARS-CoV-2 S result at screening; both as a continuous variable and categorical: negative (≤ 0.79 U/mL) vs. positive (> 0.79 U/mL); additionally, categorized as ≤ 0.79 U/mL, > 0.79 U/mL through 50 U/mL, > 50 U/mL through 200 U/mL, > 200 U/mL
- History of prior SARS-CoV-2 infection at Screening
- Time (in weeks) from previous vaccine series
- Additional IS medications
- Steroid dose
- For Stage 2: previous vaccine series
- Medication dose for or Cohort A: MMF or MPA and Cohort B: MTX
- For Cohort C and Cohort F: B cell depletion therapy:
 - Type of B cell depletion therapy
 - Time (in weeks) from last dose of b cell depletion therapy to vaccine.
 - CD19+ B cells

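### Vaccine-type comparisons within Cohorts C and F are unrandomised, and the planned models have no term for B-cell depletion or concomitant MMF/MTX, although these values are baseline variables

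*Protocol*

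**What the plan says.** **Model.** Protocol 13.4.3 specifies a logistic model with age group, cohort, vaccine and IS treatment plan, plus disease type and antibody negative/positive status after the initial regimen. A linear model is used for antibody level. Section 13.4.4 draws the vaccine-type contrasts from these models, adds baseline corticosteroid dose, and says: "Additional covariates for disease activity, co-morbid illness, age, and sex may be added". Its last paragraph repeats the plan for Stage 2. SAP 8.2.4 gives the same base model.

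**Assignment.** In Cohort C the study vaccine is the one already used for the initial series (Protocol 3.1.1.1, 3.1.2.1). In adult Cohort F it depends on previous doses and, after three doses of one mRNA vaccine, on the participant's choice (3.1.1.2). In pediatric Cohort F it depends on the previous vaccine (3.1.2.2).

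**Case mix.** Cohorts C and F admit anyone treated within the past 18 months: "Participants taking B cell depletion medications, regardless of whether they are also taking MMF or MTX, will be placed in this cohort".

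**Data.** For Cohorts C and F, SAP 6.2 lists type of B-cell depletion therapy, "Time (in weeks) from last dose of b cell depletion therapy to vaccine", and CD19+ B cells. Additional IS medications are listed for everyone. All of these are for baseline summaries. Protocol 8.1.4.4 draws CD19+ cells only from participants on a CD20-depleting agent. Protocol 2.3 has an exploratory objective relating baseline CD19 count to response in the B-cell-depletion cohort.

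**The concern.** Whether response differs by vaccine type is a secondary objective in both stages (Protocol 2.2.1, 2.2.2), and Section 13.7 gives power for between-arm comparisons. Within Cohorts C and F, nothing in the design balances B-cell status across vaccines. The protocol's background (1.1, 1.2.1, 13.7) names B-cell depletion and mycophenolate as reasons for poor response, so both are plausible strong predictors.

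Stage 2 gives a specific route to imbalance. Arm F4 (Sanofi-GSK) takes newly recruited people with many previous doses, and also participants from F2 (alternative mRNA) whose Elecsys result was still at or below 2500 U/mL. F4 may therefore hold people with deeper or more recent depletion than F2.

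If so, an mRNA versus Sanofi-GSK difference, or a Moderna versus Pfizer difference in Cohort C, could be produced or hidden by case mix that the trial has recorded but not modelled.

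**Working it through.** **1. The plan's own figures.** Protocol 13.7 states: "A sample size of 33 evaluable participants achieves at least 90% power". With a null rate of 0.25, a true rate of 0.5 and a one-sided exact test, the rule is to reject at 13 or more responders of 33. P(X ≥ 13 | 0.25) = 0.0484 and P(X ≥ 13 | 0.5) = 0.919, so the statement reproduces. The single-arm comparison (0.25 v 0.584, 33 per arm) has odds ratio (0.584/0.416)/(0.25/0.75) = 4.21. Two-sided power with pooled variance is Φ[(0.334 − 1.96 × 0.1214)/0.1142] = 0.80, which also reproduces.

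**2. Covariates planned against covariates recorded.**

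| Baseline value (SAP 6.2) | In the 13.4.3/13.4.4 or SAP 8.2.4 model? |
|---|---|
| Disease type | Yes |
| Antibody negative/positive | Yes |
| Steroid dose | Added in 13.4.4 |
| Age, sex | Optional |
| Weeks since last B-cell-depleting dose | No |
| CD19+ B cells | No (exploratory association only) |
| Additional IS medications (MMF/MPA, MTX in C and F) | No |

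**3. Assumptions (not in the documents).** One binary covariate X, such as recent depletion, has an odds ratio for response of 3, 6 or 10 and about 50% prevalence. The imbalance is 20 points: 40% v 60% have the favourable level. The 40% arm has a response rate of 0.25. Sizes are 33 per arm (the protocol's evaluable number) and 66 (2 × 33, both Elecsys subgroups together).

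**4. Spurious odds ratio with no vaccine effect.** Let p0 and p1 be the response rates without and with the favourable level. Solve 0.4·p1 + 0.6·p0 = 0.25 at the given odds ratio. The other arm then has rate 0.6·p1 + 0.4·p0.

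| Odds ratio of X | p0, p1 | Arm rates | Apparent vaccine odds ratio |
|---|---|---|---|
| 3 | 0.167, 0.375 | 0.25 v 0.292 | 1.24 |
| 6 | 0.119, 0.447 | 0.25 v 0.316 | 1.38 |
| 10 | 0.088, 0.492 | 0.25 v 0.331 | 1.48 |

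**5. False-positive rate** (logistic simulation, 4,000 trials per setting, two-sided 5%).

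| Odds ratio of X | 33 per arm, without X / with X | 66 per arm, without X / with X |
|---|---|---|
| 3 | 6.2% / 4.6% | 8.5% / 5.2% |
| 6 | 8.1% / 4.5% | 12.3% / 4.4% |
| 10 | 10.4% / 5.0% | 16.9% / 4.9% |

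**6. Power with X balanced,** 0.25 v 0.584, 33 per arm: 80.4% to 82.2%, 79.8% to 84.1% and 80.1% to 86.2% for X odds ratios of 3, 6 and 10. The gain is 2 to 6 points.

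**7. A true difference with X imbalanced** (conditional vaccine odds ratio 4.2, X odds ratio 6, 33 per arm). If the better vaccine has the less favourable case mix, rejection is 39.5% without X and 65.2% with it. If it has the more favourable mix, rejection is 85.2% without X and 69.8% with it; the excess is bias, not power.

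Neither simulated model includes disease type or antibody status, which the planned model does. If these track X, they remove part of the bias, so the figures in steps 4 and 5 lean high for a given X.

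**The case against.** **The comparisons are exploratory and the SAP is unfinished.** SAP 8.1.4 makes all secondary analyses descriptive without multiplicity control. SAP 8.4, 8.5 and 10 defer detail, and the SAP is to be finalised before database lock. This stands: no controlled error rate is breached, and there is still time. It does not supply the missing terms, because the base model is written out in both documents without them.

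**Nothing shows that vaccine groups differ in B-cell status.** This is correct for Moderna versus Pfizer in Cohort C. For F2 versus F4 the entry rules make a difference plausible, but its size is unknown.

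**A reader might extend the point to drug-class contrasts,** since 13.4.4 says "Type of IS medications will be compared within and across each type of vaccine". The documents do not support that for time since depletion or CD19. Time since depletion is undefined in Cohorts A, B, D and E, and CD19 is not scheduled there. Both describe the B-cell-depletion exposure itself, so adjusting for them would remove part of what is compared. Only concomitant MMF/MTX mixes the classes. It does so mainly in Cohort C, because Cohort F users withhold these drugs around vaccination (Protocol 7.1.1).

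**A reader might infer that the depletion date is not captured,** because Protocol 13.4.5 says that medications "beginning 30 days before the Screening Visit and continuing throughout the study will be collected". That sentence concerns the general medication summary. Eligibility requires an 18-month B-cell-depletion history (4.2.1.1.1), SAP 6.2 plans weeks since last dose, and SAP 6.3 names a separate Immunosuppressive Medication form.

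**A larger effect is tempting.** With response of 10% v 60% by CD19 status (odds ratio 13.5) and a 40/60 split, simulated false positives are 14-22%. The documents do not give that contrast. An assumed antibody proxy in the model lowers a re-run of this scenario from 16-22% to about 11-16%. The power gain simulated there (50% to 61% at 33 per arm) is for marginal rates of about 0.35 v 0.59, not the protocol's 0.25 v 0.584.

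**Conclusion.** The point holds for vaccine-type contrasts within Cohorts C and F. They are unrandomised, and the written models omit B-cell-depletion and concomitant MMF/MTX terms that could be built from variables in SAP 6.2. Confounding is the main issue; lost power is secondary and modest when the covariate is balanced.

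The size rests on an assumed covariate effect and imbalance. Over odds ratios of 3 to 10 with a 20-point imbalance, false positives run at about 6-10% (33 per arm) or 9-17% (66 per arm) against a nominal 5%. With no imbalance there is no bias, and power rises from about 80% to 82-86%.

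The primary per-arm exact tests use no covariates and are unaffected, as is the randomised continue-versus-withhold contrast in Cohorts A and B. This is worth changing because it is cheap, not because a main conclusion depends on it.

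**What to change.** In the next SAP version:

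- For vaccine-type contrasts within Cohorts C and F, prespecify two covariates nested in those cohorts: weeks since last B-cell-depleting dose, and concomitant MMF/MPA or MTX (yes/no).
- Repeat these contrasts with Week 0 CD19+ status (detectable / undetectable / not measured) as a sensitivity analysis. The third level is needed because CD19+ cells are drawn only for CD20 agents. Keeping CD19 out of the main model limits collinearity with time since dose and sparse cells at about 33 per arm.
- For drug-class contrasts, do not adjust for time since depletion or CD19. Also report the B-cell-depletion group without concomitant MMF/MPA or MTX users, which matters mainly in Cohort C.
- State that adjustment reduces confounding but does not make these comparisons randomised.

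The cost is SAP wording and a few model degrees of freedom. The values are already planned baseline variables, so no new data collection is needed.

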- Stage 1 participant rolls over to Stage 2
 - A Stage 1 participant who has a Roche Elecsys result ≤ 2500 U/mL at a post-Baseline visit may elect to roll over into Stage 2, starting the Stage 2 schedule of events for rollovers.
- Stage 2 participant rolls over to a different Stage 2 treatment arm
 - A Stage 2 participant who received an alternative mRNA vaccine dose and has a Roche Elecsys result ≤ 2500 U/mL at a post-Baseline visit may elect to re-enter Stage 2, restarting the Stage 2 schedule of events for rollovers.

Rollover participants will be evaluated for Stage 2 eligibility per Section 4.2.1.2.2 Inclusion and Exclusion Criteria for Adult Stage 2 Rollover Participants.

Participants will be allocated to 1 of 3 cohorts based on their IS regimens:

- Cohort D: Receipt of MMF or MPA (\pm other rheumatic disease medications, including biologics)
 - Participants who are taking MMF or MPA (without additional B cell depleting medications or MTX) will be placed in this cohort.
- Cohort E: Receipt of MTX (\pm other rheumatic disease medications, including biologics)
 - Participants who are taking MTX (without additional B cell depleting medications or MMF/ MPA) will be placed in this cohort.
- Cohort F: Receipt of BCDT within the past 18 months (\pm other rheumatic disease medications)
 - Participants taking B cell depletion medications, regardless of whether they are also taking MMF or MTX, will be placed in this cohort.

Treatment Arms: [Table 3](#) describes the vaccines available to newly recruited participants and [Table 4](#) describes the vaccines available to rollover participants depending on the previous COVID-19 vaccines they received. Participants in Cohorts D, E, and F will receive a dose of an alternative COVID-19 vaccine compared to their previous COVID-19 vaccine doses. Originally, participants who previously received 3 total doses of a single mRNA vaccine (Moderna COVID-19 Vaccine OR Pfizer-BioNTech COVID-19 Vaccine) received their choice of either the Janssen vector-based COVID-19 vaccine or the other mRNA COVID-19 vaccine, and participants who previously received 2 doses of the Janssen vector-based COVID-19 vaccine received the Moderna COVID-19 Vaccine.

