Update: Beginning with v4.0 of the protocol, this trial will not utilize the Janssen vector-based COVID-19 vaccine. Participants who previously received 3 total doses of a single mRNA vaccine will receive their choice of an alternative mRNA COVID-19 vaccine or the Sanofi-GSK protein-based COVID-19 vaccine. Participants who previously received 4 or more doses of a single mRNA vaccine or 3 or more doses of a mixture mRNA vaccines (Moderna COVID-19 Vaccine AND Pfizer-BioNTech COVID-19 Vaccine, in any order or combination) will receive the Sanofi-GSK protein-based COVID-19

vaccine. Beginning with v6.0 of the protocol, bivalent versions of the mRNA vaccines, Moderna and Pfizer-BioNTech COVID-19 vaccines, replaced original monovalent versions.

Participants in Cohorts D and E will withhold their cohort-defining IS medications before and after the alternative vaccine dose per protocol instructions (see Section 7.1.1 Protocol-mandated Medications).

Participants in Cohort F who are taking MMF, MPA, or MTX in addition to BCDTs will withhold these medications before and after the alternative vaccine dose per protocol instructions (see Section 7.1.1 Protocol-mandated Medications).

All potential treatment arms for Adult Stage 2 are detailed in [Table 5](#).

Schedule of Events: Visits to assess endpoints will occur at Baseline (Week 0), Week 4 ± 1 week, Week 12 ± 2 weeks, Week 24 ± 2 weeks, Week 36 ± 2 weeks, and Week 48 ± 2 weeks. Participant and study flow diagrams for Stage 2 are provided in Figure 3 and Figure 4, respectively.

A participant who is newly recruited to the study for entry into Stage 2 may be on study for up to a maximum of 13 months. A participant who enters Stage 2 after a serologic negative, suboptimal, or low immune response to their Stage 1 vaccine dose may be on study for up to a maximum of 26 months. Rollover participants will discontinue follow-up as part of Stage 1 upon rollover into Stage 2. A participant who rolls over to a different Stage 2 treatment arm after a serologic negative, suboptimal, or low immune response to another Stage 2 vaccine dose may be on study for up to a maximum of 38 months.

Table 3. Vaccines Available to Adult Stage 2 Newly Recruited Participants

Previous Vaccines Received	Vaccine Option for Study Treatment Stage Two: First Dose
3 doses of the same mRNA COVID-19 vaccine	A choice of an alternative mRNA COVID-19 bivalent vaccine OR Sanofi-GSK COVID-19 Vaccine

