	Pfizer-BioNTech COVID-19 vaccine (from Arms A2P or A5P, or newly recruited) Ages 2-17	ARM D2P	Moderna COVID-19 Vaccine
Cohort E: Methotrexate	Moderna COVID-19 vaccine (from Arms B1P or B4P, or newly recruited) Ages 12-17 only	ARM E1P	Pfizer-BioNTech COVID-19 Vaccine
	Pfizer-BioNTech COVID-19 vaccine (from Arms B2P or B5P, or newly recruited) Ages 2-17	ARM E2P	Moderna COVID-19 Vaccine
Cohort F: B cell depletion therapy	Moderna COVID-19 vaccine (from Arms C1P, or newly recruited) Ages 12-17 only	ARM F1P	Pfizer-BioNTech COVID-19 Vaccine
	Pfizer-BioNTech COVID-19 vaccine (from Arms C2P or newly recruited) Ages 2-17	ARM F2P	Moderna COVID-19 Vaccine

*Bivalent vaccines will be administered per Section 6, Investigational Agents

Figure 7. Participant Flow Diagram for Pediatric Stage 2

[figure not shown]
[figure not shown]

Figure 8. Study Flow Diagram for Pediatric Stage 2

Pediatric Stage 2: Additional alternative vaccine

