3.5.2 Pediatric Population

3.5.2.1 Pediatric Stage 1

Participants and their legal guardian(s) who sign the consent and assent forms, as appropriate to age, and meet all eligibility criteria for Pediatric Stage 1 will be assigned to cohorts defined by IS medication (Cohort A: MMF/MPA; Cohort B: MTX; and Cohort C: BCDT) and by the initial COVID-19 vaccine regimen received. Participants in Cohort C will be allocated to continuing to take their prescribed IS medications throughout the trial. Participants in Cohorts A and B will be randomized in a balanced fashion (1:1), within the cohorts defined by IS medication and initial COVID-19 vaccine regimen, to one of the available IS medication treatment plans (continue IS vs. withhold IS). Randomization will be performed using a permuted block design stratified by disease type.

A total of 80 participants with a Roche Elecsys® Anti-SARS-CoV-2 S result ≤ 2500 U/mL will be randomized or allocated to each arm. In each arm, the number of participants with Roche Elecsys® Anti-SARS-CoV-2 S results ≤ 200 U/mL will be

capped at 40 participants, and the number of participants with Roche Elecsys® Anti-SARS-CoV-2 S results >200 U/mL and ≤ 2500 U/mL will be capped at 40 participants.

3.5.2.1 Pediatric Stage 2

Participants who have signed the informed consent and assent forms, as appropriate to age, and meet all eligibility criteria for Pediatric Stage 2 will be allocated to cohorts defined by IS medication (Cohort D: MMF/MPA; Cohort E: MTX; and Cohort F: B cell depletion therapy) and by the previous COVID-19 vaccine regimen (Pfizer-BioNTech COVID-19 Vaccine in ages 2 through 17 years or Moderna COVID-19 Vaccine in ages 12 through 17 years). Participants in Cohort D will withhold their MMF/MPA, participants in Cohort E will withhold their MTX, and any participants in Cohort F (B cell depletion therapy) who are also taking MMF/MPA or MTX will withhold these medications. No randomization will be employed.

A total of 80 participants with a Roche Elecsys® Anti-SARS-CoV-2 S result ≤ 2500 U/mL will be allocated to each arm. In each arm, the number of participants with Roche Elecsys® Anti-SARS-CoV-2 S results ≤ 200 U/mL will be capped at 40 participants, and the number of participants with Roche Elecsys® Anti-SARS-CoV-2 S results > 200 U/mL and ≤ 2500 U/mL will be capped at 40 participants.

4. Selection of Participants and Clinical Sites

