8.2.2.1.2 Pre-Screening for Adult Stage 2 Rollover Participants

Elecsys® Anti-SARS-CoV-2 S assay results for study participants from visits at Week 4 through Week 48 will be reviewed when received by study sites. Participants with a negative, suboptimal, or low immune response at any visit following receipt of the previous COVID-19 vaccine dose will have the data from their last study visit pre-screened to determine if they may qualify for Stage 2.

If a participant pre-screens successfully for Stage 2, the study site will contact the participant to offer them the opportunity to be fully screened for Stage 2.

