$$\text{Fold improvement} = \frac{\text{anti-COVID-19 Antibody Response Week 4}}{\text{anti-COVID-19 Antibody Response Baseline}}$$

Longitudinal changes in the anti-COVID-19 antibodies will be summarized over time by study visit using descriptive statistics. Details on handling missing data and intercurrent events, which result in anti-COVID-19 antibody response data being unevaluable for immune response, will be outlined in the statistical analysis plan.

Longitudinal changes in neutralization and pseudoneutralization assays will be summarized by study visit using descriptive statistics. For secondary continuous efficacy endpoints, descriptive statistics will be used to summarize the distribution of scores in each arm; for adult participants, this will include the H-SLEDAI (SLE participants), Tender/Swollen Joint Count (RA participants), PDAI (pemphigus participants), modified Rodnan Skin Score (SSc participants), CGI-C, PtGA, PGI-C, PGA, and PROMIS 29, and for pediatric participants, this will include the SLEDAI-2K (SLE), Tender/Swollen Joint Count (JIA participants), MMT-8 and CMAS (JDM participants), CGI-C, PtGA, PGI-C, PGA, and PedsQL. The proportion of participants who meet definition for disease-specific flares, including the Thanou modified SELENA-SLEDAI Flare Index (SLE participants), patient-reported flare assessment (SSc participants), and physician-assessed relapse (MS participants), will be summarized. The disease-specific flare endpoints will include Thanou modified SELENA-SLEDAI Flare Index (SLE participants), DAS28-CRP (RA participants), patient-reported flare assessment (SSc participants), flare assessment (pemphigus participants) and physician-assessed relapse (MS participants) in adults and the ACR Provisional Criteria for Global Flare in Childhood-onset SLE (for SLEDAI; pediatric SLE participants), physician-assessed relapse (POMS participants), and flare assessment (JDM participants).

Descriptive statistics will be used to summarize the proportions of participants in the safety arm who experience safety endpoints.

For Stage 2, analysis plans for primary and secondary endpoints will be repeated to evaluate the immune response to a subsequent alternative COVID-19 vaccine dose and to determine whether immunologic variables are associated with increased disease activity.

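### By-visit antibody summaries to Week 48 do not account for rollover triggered by a low titre; visit levels in arms with a rollover route would usually be biased upward

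*Protocol*

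**What the plan says.** - **Endpoint and method.** Protocol 3.3 lists change in antibody from Week 0 to Weeks 4, 12, 24, 36 and 48 as a secondary endpoint, and neutralization likewise. Protocol 13.4.4: "Longitudinal changes in the anti-COVID-19 antibodies will be summarized over time by study visit using descriptive statistics". SAP 8.3.3 and 8.3.4 plan the same, and SAP 8.2.4 adds by-visit plots for each arm.
- **Exit rule.** Protocol 3.1.1.2 sets the current threshold at 2500. A Stage 1 participant with a Roche Elecsys result at or below 2500 "U/mL at a post-Baseline visit may elect to roll over into Stage 2". An adult given an alternative mRNA dose in Stage 2 may re-enter on the same threshold, "restarting the Stage 2 schedule of events for rollovers". Protocol 8.2.2.1.2 covers "Participants with a negative, suboptimal, or low immune response at any visit following receipt of the previous COVID-19 vaccine dose"; protocol 8.4.2.1.2 is the pediatric counterpart.
- **Consequence of exit.** "Rollover participants will discontinue follow-up as part of Stage 1 upon rollover into Stage 2" (adults; the pediatric text agrees). For Stage 2 re-entry, the end of the first course is inferred from the schedule restarting. Analysis populations are separate by stage (protocol 13.4.1).
- **Handling.** Protocol 13.4.2 names monoclonal antibodies, plasma products and SARS-CoV-2 vaccine given outside the study, all for Week 4 data. For later visits, protocol 13.4.4 says that missing data and intercurrent events "which result in anti-COVID-19 antibody response data being unevaluable for immune response, will be outlined in the statistical analysis plan". SAP 8.3.3 and 8.3.4 defer to later SAP versions.
- **Missing data.** SAP 8.3.1 extends the seroconversion definition through Week 48 and treats missing antibody data as MCAR. SAP 8.3.2 leaves missing fold-increase data unimputed. SAP 6.1 plans rollover counts, but not by visit.

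**The concern.** Exit depends on a version of the variable being summarised. If some of those with low titres leave after each visit, the mean, median or geometric mean at the next visit is taken over those who stayed, while the Week 4 value is taken over everyone. The visit curve then mixes real waning with selection. A reader of the by-visit plots would usually see slower waning than occurred, by an amount that differs between arms with their titre distribution, rollover uptake and free destination places.

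The same fact contradicts the MCAR statement for seroconversion after Week 4, because absence that depends on an observed titre is not completely at random.

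Scope is limited. No onward route is stated for the Sanofi-GSK arms, for pediatric Stage 2, or for children aged 2 to 11 who were primed with Moderna (protocol Tables 8 and 9).

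**Working it through.** The documents state no figure for this endpoint, so there is nothing to reproduce. They also give no uptake, titre spread or decay rate. The check is a simulation on assumed inputs.

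**Inputs from the protocol.** Threshold 2500 U/mL (3.1.1.2). Destination arm D2P takes participants "from Arms A2P or A5P, or newly recruited" (Table 9). Source pool: 80 + 80 = 160. Destination: 80 places, 40 at or below 200 U/mL and 40 above (3.5.2).

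**Assumed.** Week 4 log10 titre: mean 2.8, SD 1.0. Decay 0.05 log10 per month. Within-person SD 0.2. After each visit, a participant at or below the threshold leaves with probability p if a place is free in that titre stratum.

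**True ratio.** 44 weeks / 4.345 = 10.13 months, and 10^(−0.05 × 10.13) = 0.312.

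**Apparent ratio** = geometric mean at Week 48 in those still followed / geometric mean at Week 4 in everyone. Threshold 2500:

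| Uptake p per qualifying visit | Share of pool leaving | Apparent ratio | Apparent / true |
|---|---|---|---|
| 0 | 0 | 0.312 | 1.00 |
| 5% | about 15% | 0.360 | 0.360/0.312 = 1.15 |
| 10% | about 27% | 0.425 | 0.425/0.312 = 1.36 |
| 30% | about 50% | 0.848 | 0.848/0.312 = 2.72 |

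At 10% uptake, a true fall of 69% (1 − 0.312) would read as about 58% (1 − 0.425).

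**Variations.**
- The SAP's older threshold of 200, from its summary of protocol v3.0, gives 0.370, 0.435 and 0.663 at 5%, 10% and 30%.
- At 2500 and 30%, the ratio is 0.755 if only the total of 80 binds. If new recruits take half the places, it is 0.360, 0.414 and 0.464 at 5%, 10% and 30%.
- With faster decay (truth 0.17), the ratio is 0.20–0.21, 0.23–0.25 and 0.36–0.46.
- Without stratum caps, the bias was upward in all 864 scenarios of a wider grid.
- With caps and low titres (Week 4 mean 2.0, SD 0.6–1.0), the places at or below 200 fill first. Exits then come from higher titres, and the ratio is 0.29–0.35 at 10% and 0.25–0.29 at 30% (truth 0.31). Hence usually, not always.

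**Paired Week 48/Week 4 change in those remaining.** 0.308–0.311 against 0.312. If higher titres decline faster, it overstates waning somewhat (median 0.92 times the true ratio on the wider grid).

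**Change from Week 0.** If lower titres leave, the direction follows the sign of (Week 4 SD − correlation × Week 0 SD):
- 1.0 − 0.6 × 0.8 = +0.52: overstated.
- 0.6 − 0.8 × 1.0 = −0.20: understated.

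No size is given. The Week 0 distribution used in these runs (mean 1.3, SD 0.8) puts only about 11% above 200 U/mL, since (2.301 − 1.3)/0.8 = 1.25, whereas a full 40/40 arm holds half there. With a Week 0 that fits the strata, the level bias keeps its direction (0.36–0.49 at 5–10% uptake).

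**Seroconversion at Week 48 in Week 0 negatives.** −2 to +2 percentage points if uptake is equal; +5 to +7 if negatives leave at 30% and positives at 10%.

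**Does a model help?** With 70 participants and capped exit at 10% and 30%, raw ratios were 0.43–0.78. A likelihood-based repeated-measures model gave 0.31 (truth 0.31). For a second assay correlated 0.7–0.9 with Elecsys, raw was 0.39–0.75, the model without Elecsys 0.313–0.318 and with it 0.311–0.312 (truth 0.312). These data were generated so that exit depends only on observed titres, so the recovery is expected.

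**The case against.** The strongest reply is that the plan is unfinished here and has not chosen wrongly. Protocol 13.4.4 sends the question to the SAP, SAP 8.3.3 and 8.3.4 promise later detail, and SAP section 2 commits to updates before database lock. The list in protocol 13.4.2 is not exhaustive. This stands: it is a deferred gap. But rollover from Stage 1 was already in protocol v3.0, which the SAP summarises, so it could have been named. The one missing-data assumption the SAP states in a section reaching Week 48 is MCAR.

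The MCAR sentence does sit under a Week 4 heading, and its effect has no fixed direction when uptake is equal. That limits its weight, but titre-triggered exit still contradicts it at later visits.

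A while-on-stage summary is also a legitimate target, since populations are separate by stage. That stands too, provided it is labelled and the numbers are shown.

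Finally, the listed endpoint is change from Week 0, no objective names durability, and SAP 8.1.4 makes secondary analyses exploratory. A reader might infer that the trial will overstate durability throughout, or that a test or the primary result is compromised. The documents do not support this. The upward bias concerns unpaired visit levels and can reverse, change from Week 0 can go either way, and rollover follows the Week 4 visit.

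**Conclusion.** The point holds for unpaired by-visit levels to Week 48 in arms with a rollover route. Followed as written, the plan summarises a titre-selected remainder, usually with upward bias, and rollover is not named as an event to be handled. Only the mechanism and the omission come from the documents. The size rests on assumed titres, decay and uptake: an apparent ratio of about 0.36–0.37 at 5% uptake and 0.43–0.44 at 10% against a true 0.31, the upper figures being for the SAP's older threshold. It can be much larger at high uptake and slightly below the truth in low-titre arms. This should be settled before database lock, but it does not threaten the trial's main conclusions.

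**What to change.** In SAP 8.3.3 and 8.3.4, with a matching line in protocol 13.4.4:

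1. Name rollover, and re-entry within Stage 2, as an intercurrent event.
2. Keep the raw visit summaries and the SAP 8.2.4 plots, label them while-on-stage, and show numbers remaining and rolled over by arm and visit.
3. Beside them, report visit means and change from Week 0 by arm from a likelihood-based repeated-measures model on log titre, using all pre-rollover values. The target is the course after that stage's dose had no rollover occurred. Include the triggering Elecsys value when other assays are modelled; its numerical gain was small in the runs above, but it makes missing at random more credible. Keep the LLOD/2 rule.
4. Add a simple sensitivity analysis that shifts the post-rollover values.
5. In SAP 8.3.1, replace the MCAR statement for rollover participants at visits after Week 4.

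The cost is SAP wording and modest programming, with no new data; Elecsys is already scheduled at each clinic visit from Week 4. The downside is reliance on a model and on missing at random given observed titres. The choice to roll over may also depend on unmeasured factors, which is why step 4 is needed.
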